Hypothesis: Fecal microbiota transplantation will result in a sustained repopulation of the patient's microbiome that corresponds to the bacteria from the donor stool.

III. Methods and Study Design

This is a randomized controlled pilot study to assess the safety and to measure the microbiological and clinical impacts of FMT in patients with obesity. We will continue to prospectively enroll and screen adult patients until 20 patients have completed all study visits. We anticipate total enrollment to be 50 patients to account for screen fails and dropouts. Eligible patients are those who are obese (BMI of 35 kg/m² or greater). Patients will be randomized 1:1 to receive FMT or placebo. The participants will receive either an FMT from a lean healthy donor using 30 induction FMT capsules or placebo capsules. The participants will continue to receive a monthly maintenance dose of 12 FMT oral capsules or placebo at week 4 and week 8. Serum for hormone levels will be collected at baseline, weeks 1, 4, 6, 8 and 12. Stool for microbial assessment will be collected at baseline and weeks 1, 4, 6, 8, 12, 26, and 52. A Food Frequency Questionnaire will be taken by the patient at week 0. Donor Stool will be obtained from OpenBiome. OpenBiome is a nonprofit 501(c)(3) organization that provides hospitals with screened, filtered, and frozen material ready for clinical use (See Attachments for OpenBiome Quality and Safety Program as well as donor screening examples).

Primary Safety Endpoint:

Safety Endpoints: Number and nature of adverse events at week 1, 6, 12 and 26.

Primary Clinical Endpoint:

The primary clinical end point is an increase in the AUC for GLP-1 after a mixed meal test from baseline and 12.

Secondary Endpoints:

- Microbial Endpoints: Recipients fecal microbial diversity at week 6 and 12 compared to baseline
- Clinical Endpoints: Decrease in BMI and waste circumference at week 6 and 12 compared to baseline.

Trial Treatment:

The treatment for this trial will be administration of an induction dose of 30 FMT capsules ingested orally. Treatment will occur after screening.

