4. Baseline blood work to assess for sequela of obesity: insulin, LFTs, CBC, and HgA1C and fasting serum lipids and blood glucose
5. Stool sample to exclude current infections (bacterial culture, ova & parasites, Clostridium difficile toxin) and a sample for high-throughput 16S rRNA sequencing and metabolomics.
6. Urine Pregnancy Test for females of child-bearing age: Women of child-bearing potential will be counseled by study clinicians that those randomized to the treatment arm will be requested to avoid pregnancy by hormonal or barrier methods from randomization for 4 months (duration of FMT therapy and one month lag afterwards).
7. Diet recall and question about specific dietary restrictions or preferences. The patients will be asked to maintain their standard diets throughout the study.
8. Baseline levels of ghrelin, Leptin, PYY and adiponectin will be measured
9. A mixed meal tolerance test will also be performed. GLP-1, leptin and PYY measurements will be taken at time 0, 15, 30, 45, and 60 minutes.
10. Pre FMT screening labs including HIV, Hepatitis B and C and Syphilis
11. Serum will also be collected for metabolomic profiling
- 12: Test swallow of an empty capsule
13. Indirect Calorimetry – see Appendix 7
14. Patients will be sent home with 9 doses of a proton pump inhibitor to be taken 48 hours 24 hours prior to and the day of each capsule administration (3 times total).

Week 0: (Treatment and Control Arms): Randomization: Eligible patients will be randomized 1:1 according to a computer-generated randomization list. The randomization will be held centrally at the Brigham and Women's Hospital Research Pharmacy. The treatment location will be masked to the patient and investigators performing data analysis. The health care worker administering FMT or placebo will not be aware of the treatment being administered. Treatment will be administered based on the result of randomization.

- Food Frequency Questionnaire
- Stool transplant (or Placebo) via capsule induction
- A proton pump inhibitor will be taken daily at 48 hours and 24 hours prior to and day of capsule consumption.

Week 1: (Treatment and Control Arms): Follow up and adverse event screening. Additionally:

- BMI, Iliac measurements, hip to waist ratio
- Indirect Calorimetry
- Stool for microbiome analysis and metabolomics
- CBC, LFTs, FBG, HgA1C, lipids, glucose, metabolomics
- diet recall
- Symptom Diary Card and Adverse Event screening

Weeks 2-12: (Treatment and Control Arms)

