Symptom diary Cards will be filled out weekly for adverse event monitoring

Week 4, 8 (Treatment and Control Arms): Monitored Capsule Consumption and Follow-up study visits for assessment of:

- Ingestion of 12 FMT capsules or inactive placebo.
- A proton pump inhibitor will be taken daily for the 48 hours 24 hours prior to and day of capsule consumption.
- BMI, Iliac measurements, hip to waist ratio
- Stool for microbiome analysis and metabolomics
- CBC, LFTs, FBG, HgA1C, lipids, glucose, metabolomics
- diet recall
- Symptom diary Card and Adverse Event screening

Weeks 6, 12 : Follow-up study visits for assessment of:

- BMI, Iliac measurements, hip to waist ratio
- Stool for microbiome analysis and metabolomics
- CBC, LFTs, FBG, HgA1C, lipids, glucose, metabolomics, ghrelin and leptin, PYY and adiponectin
- Mixed meal tolerance test followed by serum for GLP-1, Leptin and PYY at time 0, 15, 30, 45, and 60
- diet recall
- Indirect Calorimetry
- Symptom Diary Card and Adverse Event screening

Week 26 and 52:

- Safety assessment and Symptom Diary Cards via phone interview by a physician to screen for adverse events.
- Stool sample for microbiome analysis to be mailed in
- Ask for the patients current weight

Stool collection instructions are outlined in Appendix 2.

Patient obligations in the study will end at week 52 however the patient's medical record may be followed prospectively for evaluation of weight loss and weight loss surrogates as well as metabolic parameters done for clinical care through year 5 post-enrollment as needed. This may include review of partner's available records or records from home provider. (when applicable)

Stopping Criteria

Adverse events will be specifically monitored at week 1, 4, 6, 8, 12, 26, and 52 after FMT by direct patient interviews, or by reporting from clinical sites of adverse events at any time in-between. A data safety and monitoring board (DSMB, Appendix 5) will review all patient data to ensure optimal patient safety and precautions for subjects with obesity treated with FMT. A severity grade for adverse events (Appendix 6) and subject symptom diary cards will be used (Appendix 7). The DSMB will meet a minimum of 2 times: after treatment of the first 10 subjects, and after treatment of all 20 subjects. Study will be stopped under the following circumstances;

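### The week-12 GLP-1 AUC comparison should be adjusted for the baseline AUC already collected; at about 10 per arm this narrows the interval unless the baseline to week-12 correlation is very high

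*Combined protocol and SAP*

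**What the plan says.** Section III gives the primary clinical endpoint as follows: "The primary clinical end point is an increase in the AUC for GLP-1 after a mixed meal test from baseline and 12". The secondary endpoints are also set against baseline: "Decrease in BMI and waste circumference at week 6 and 12 compared to baseline" for the clinical ones and "Recipients fecal microbial diversity at week 6 and 12 compared to baseline" for the microbial one.

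The baseline measurements are planned. Section IV.A lists a mixed meal test at screening ("GLP-1, leptin and PYY measurements will be taken at time 0, 15, 30, 45, and 60 minutes") and repeats it at weeks 6 and 12 ("Mixed meal tolerance test followed by serum for GLP-1, Leptin and PYY at time 0, 15, 30, 45, and 60"). Stool for 16S sequencing is also taken at screening.

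On size, Section III says "Patients will be randomized 1:1 to receive FMT or placebo" and that enrolment continues "until 20 patients have completed all study visits".

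Section VIII calls the study exploratory, makes safety the main objective, and gives estimation of effect sizes for larger studies as a secondary purpose. It names no test, model, between-arm contrast or covariate. It gives no significance level, power, standard deviation or correlation.

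**The concern.** With endpoints worded as change and nothing further in Section VIII, the simplest reading is that each patient's change is computed and the arms are compared on it. That subtracts the whole baseline value. If a single meal-test AUC is only moderately correlated with the value 12 weeks later, subtraction adds baseline noise to the comparison. A chance difference between arms at baseline also carries into the change with the opposite sign.

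With about 20 evaluable patients, precision is scarce, and Section VIII wants usable effect-size estimates for later trials. Leaving the choice open would also allow adjusted or unadjusted results to be preferred once both are known.

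**Working it through.** There is no power or precision figure in the plan to reproduce; the 20 completers are a target without a calculation.

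**Inputs**
- From Section III: 20 completers at 1:1, so n = 10 per arm.
- Assumed, not in the documents: equal SD at both visits (SD = 1 unit), normal data, correlation rho between 0.3 and 0.98, two-sided 5% level. For the power figures only, a true difference of 1 SD.

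**Variances of the between-arm difference**
- Plain change: 2(1 − rho) × SD² × (2/n).
- Baseline-adjusted (ANCOVA): (1 − rho²) × SD² × (2/n).
- Large-sample ratio, adjusted to change: (1 + rho)/2.
- At 10 per arm, multiply by 1 + 1/(2n − 4) = 1 + 1/16 = 1.0625 for the estimated slope.
- For interval width, take the square root and multiply by t(17)/t(18) = 2.110/2.101.

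Example at rho 0.5: 0.75 × 1.0625 = 0.797; √0.797 × 2.110/2.101 = 0.896, so the interval is about 10% narrower.

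| rho | Large-sample ratio | Variance ratio, 10 per arm | CI-width ratio | Power for 1 SD: change → adjusted |
|---|---|---|---|---|
| 0.3 | 0.65 | 0.69 | 0.835 | 43% → 57% |
| 0.5 | 0.75 | 0.80 | 0.896 | 56% → 66% |
| 0.7 | 0.85 | 0.90 | 0.954 | 78% → 82% |
| 0.9 | 0.95 | 1.01 | 1.009 | no gain |
| 0.95 | 0.975 | 1.04 | 1.022 | no gain |
| 0.98 | 0.99 | 1.05 | 1.030 | no gain |

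A simulation of 40,000 trials at each rho gave mean width ratios of 0.833, 0.894, 0.953, 1.007, 1.021 and 1.028. In a single trial the adjusted interval was the narrower one in 90%, 80% and 63% of runs at rho 0.3, 0.5 and 0.7.

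**Break-even.** On variance: 2/1.0625 − 1 = 0.88. On interval width, with the change in t quantile: 0.87.

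**Baseline imbalance.** The baseline difference between arms has SD √(2/10) = 0.447. The chance that it exceeds 0.5 SD in either direction is 26%. Given a baseline difference d, the expected change-score difference moves by −(1 − rho)d. At rho 0.5 and d = 0.5 SD this is 0.25 SD. The standard error of the change-score difference is then √(2 × 0.5 × 0.2) = 0.447 SD, so the shift is more than half a standard error.

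**BMI.** Assume a between-patient SD of 4 to 5 kg/m² and an SD of 12-week change of 1 to 2 kg/m². With rho = 1 − SD(change)²/(2 SD²), the extremes are 1 − 4/32 = 0.875 and 1 − 1/50 = 0.98. The whole range lies above the width break-even.

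**Endpoint wording.** If week-12 value = a + b·arm + c·baseline, then change = a + b·arm + (c − 1)·baseline. The treatment effect b is the same, so the change wording can stay; only the covariate is missing.

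**The case against.** The strongest reply is that Section III names endpoints, not estimators. A reader might infer that the plan commits to an unadjusted change-score analysis. It does not: Section VIII specifies no efficacy analysis at all and does not rule out adjustment, and diversity is only to be compared with baseline. This stands. The wider gap is the missing between-arm analysis, and the covariate is one part of filling it.

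A reader might also infer that adjustment sharpens all four efficacy endpoints. The documents do not support that. They give no correlation for any endpoint, and for BMI they point to a high one: exclusion criterion 10 removes patients with a recent weight change of 10 pounds or more, BMI has no upper limit, and usual diet continues. Under the SDs assumed above, adjustment gains nothing for BMI and may widen the interval by up to about 3%. Waist probably behaves similarly.

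Nor does the argument hold for every contrast. The efficiency ratio and the imbalance calculation concern a comparison between arms. If the endpoint meant within-patient change alone, they would not apply.

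Finally, low or moderate correlation for GLP-1 AUC is an assumption. At 0.7 the gain is modest. The power figures rest on a 1 SD effect and a 5% test that the plan does not contain, and they carry limited weight in a study whose main objective is safety. This limits the size of the point. It does not remove it, because effect-size estimation is a stated purpose and the covariate is already collected.

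**Conclusion.** The point holds for the primary clinical endpoint and, with the same reservation about correlation, for microbial diversity. In a between-arm comparison at about 10 per arm, adjusting for baseline narrows the 95% interval by about 17%, 10% or 5% at an assumed correlation of 0.3, 0.5 or 0.7. In variance terms, 20 completers would do the work of about 29, 25 or 22 (20 divided by 0.69, 0.80 or 0.90). There is no gain above about 0.87.

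Under a linear model, adjustment also removes the conditional bias from chance imbalance. A reader might take this to mean that the change score is biased overall. It is not: under randomization it is unbiased on average, and the shift concerns the particular imbalance that arises.

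No material precision gain should be claimed for BMI or waist. The figures assume equal SDs at both visits, normal data and exactly 10 per arm.

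**What to change.** In Section VIII, state that the primary clinical analysis compares the arms on week-12 GLP-1 AUC, or equivalently on its change from baseline, with baseline AUC as covariate, and reports the adjusted difference with its 95% confidence interval. Use the same form for microbial diversity at weeks 6 and 12. Show raw changes by arm descriptively. The same model may be used for BMI and waist for consistency, without a claim of better precision. Reporting the baseline slope and residual SD would serve the design of the next study.

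The change takes a few sentences and needs no extra visit, sample or assay. It costs one residual degree of freedom (18 to 17) and about 6% variance inflation at 20 patients, which the table above already includes.

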Subsequent FMT administration will be maintenance capsules of frozen FMT material ingested orally every 4 weeks (weeks 4 and 8). All ingestions will be undertaken in the clinic under supervision. A follow-up phone call will be undertaken 4 hours after each ingestion visit to screen for adverse events. At 48 hours and 24 hours prior to and the day of each capsule dose (regardless of group) the patient will take a single dose of 20mg of omeprazole.

Dosage Form

1. Initial dose - filtered solution of donor stool in 30 gelatin capsules at Day 0 (16500µl total).
2. Maintenance dose – twelve capsules of fecal material taken every 4 weeks (550µl of fecal material in each size 00 gelatin capsule)

Dosing Regimen

Single induction dose of 30 capsules (16500µl)

Monthly dose of 12 capsules of fecal material (total 6600µl of fecal material at week 4 and week 8)

Capsule preparations are delivered to clinical investigators in double containment shipping vessels packed with dry ice, as with non-encapsulated placebo preparations. Packaging is labeled with the same information included on non-encapsulated preparations, with the addition of a clause instructing clinicians to administer the material to patients within 90 minutes of removal from frozen storage. Patient instructions listed in Appendix 6.

Packaging

Encapsulated fecal material in freezer safe bottles will be stored in Styrofoam boxes from the Microbiome Health Research Institute at Massachusetts Institute of Technology, as described in their Drug Master File (15543).

The Placebo Treatment:

Those in the placebo arm will undergo procedures as in the active arm. They will be given 30 placebo capsules at time of induction (Day 0) and this will be followed by 12 placebo capsules each month.

Placebo Oral Capsules

Placebo capsules are prepared to support randomized, placebo-controlled studies of FMT. These capsules are prepared according to the specifications described below and utilized in studies as indicated by the study IND.

1. An autoclaved solution consisting of 80% cocoa butter, 20% glycerol and brown food coloring, without the addition of human stool, is used as a placebo control.
2. The autoclaved placebo solution is transferred to a reservoir.
3. Capsules are generated as outlined in 6-9 of section V above.
4. Each capsule is visually inspected for integrity and contamination of the outer surface. Capsules passing inspection are placed into an HDPE plastic bottle for immediate storage at -80°C.

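### The request to avoid pregnancy is limited to the treatment arm, which cannot work as worded for women who are masked to their allocation

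*Combined protocol and SAP*

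**What the plan says.** Section IV.A, Week -2, item 6, pairs a urine pregnancy test with counselling. "Women of child-bearing potential will be counseled by study clinicians", and what they are told is that "those randomized to the treatment arm will be requested to avoid pregnancy by hormonal or barrier methods from randomization for 4 months". The stated basis for the 4 months is the length of FMT therapy plus a one-month lag.

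The Week 0 entry of the same section sets out the masking: "The treatment location will be masked to the patient and investigators performing data analysis", and "The health care worker administering FMT or placebo will not be aware of the treatment being administered". The randomisation is held centrally at the research pharmacy.

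Two lines in Section III bear on how the arms are handled. Under The Placebo Treatment: "Those in the placebo arm will undergo procedures as in the active arm". Under Trial Treatment, for the acid-suppressing drug: "each capsule dose (regardless of group) the patient will take a single dose of 20mg of omeprazole".

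Elsewhere, exclusion criterion 11 in Section V removes women who are already pregnant or breastfeeding, and Section IX says that the risks in pregnancy are not known.

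**The concern.** An instruction that depends on the allocated arm is given to people who are not meant to know their arm. Two things are at stake.

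- **Masking.** The primary safety endpoint in Section III is the count and type of adverse events at weeks 1, 6, 12 and 26. Much of this information comes from the patient: direct interviews, symptom diary cards and calls after dosing ("A follow-up phone call will be undertaken 4 hours after each ingestion visit to screen for adverse events"). A woman who has worked out her arm may notice, attribute or report symptoms differently.
- **Participant safety.** The request exists because fetal risk is unknown. It protects only if the women it is meant for can tell that they are included.

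**Working it through.** No sample size, power or event figure is in dispute, so the check is mainly a comparison of texts.

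1. **Length of the request.** Item 6 gives 4 months, as therapy plus one month. Section IV describes treatment over 12 weeks: 12 × 7 = 84 days. Adding about 30 days gives 114 days, and 114 / 30.4 = 3.75 months, which rounds to 4. The duration is consistent. The difficulty is who is covered.

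2. **Who is meant to be masked, and to what.** The mask sentence speaks of treatment location. I read this as allocation: the trial uses a placebo capsule, and the person giving the capsules is kept unaware of their content. A mask on location alone would make little sense, because all ingestions are supervised in the clinic.

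3. **What is scheduled.** The only scheduled act is the Week -2 counselling. It goes to all women of child-bearing potential and comes before randomisation at Week 0, so it carries no information about anyone's arm. The visit lists for weeks 0 to 52 in Section IV.A contain no later request, by arm or otherwise. What happens after randomisation is left open.

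4. **The two ways to apply item 6 as worded.**
   - *The request is made by arm.* Every woman has already been told that it follows the treatment arm. Being asked then indicates FMT, and not being asked indicates placebo. Women in both arms can infer their allocation. All four safety endpoint time points come after randomisation, and a woman who has inferred her arm still knows it at week 26, after the 4 months have ended.
   - *No request is made.* A woman on FMT has only the conditional statement from screening, and its condition is the fact withheld from her. She cannot tell whether she is covered, and might even take silence as a sign of placebo.

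5. **Does other text extend the request to placebo?** The general line on placebo procedures does not mention contraception, whereas item 6 is specific and names one arm. Where the authors wanted an instruction to cover both arms, as with omeprazole, they said so explicitly. No visible text extends the contraception request in that way.

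6. **How many women?** The plan enrols "until 20 patients have completed all study visits" and anticipates 50 enrolled in total to allow for screen failures and dropouts. The request runs from randomisation, so the relevant base is everyone randomised, not the 20 completers. The documents give neither that number nor the share who are women of child-bearing potential. Any count would be a guess, so none is offered.

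**The case against.** The strongest reply is that no unmasking step is actually written into the protocol. The one scheduled act is universal and precedes randomisation, the randomisation is held by the pharmacy, and the capsule-giver does not know the treatment. The visible text therefore shows no route by which clinic staff would make a request by arm. This stands, and it is why the masking consequence has to be stated as conditional.

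A second reply is that the sentence can be read in a workable way. A woman who knows that allocation is 1:1, and that FMT recipients should avoid pregnancy, has good reason to behave as though the request covers her. The line on equal procedures for placebo points the same way. This softens the problem but does not remove it: the protocol leaves her to draw that conclusion and does not ask her to.

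Third, the consent form and the Appendix 1 timeline are not visible, and either may already ask all women. That is a real limit. If they do, item 6 disagrees with them and still needs correcting, but the practical risk would be small.

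A reader might also infer that women on FMT are left without protection. The documents do not support that. There is a pregnancy test at screening, an exclusion for pregnancy and breastfeeding, and counselling of every woman concerned. What remains is uncertainty about who is expected to use contraception during dosing and the month after it.

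**Conclusion.** The point holds as a defect in the wording of item 6: a rule limited to one arm either reveals allocation or fails to reach the masked women it is meant for. It is a cheap improvement and does not threaten the trial's validity.

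It would go too far to say that the protocol unmasks its participants. That happens only if someone makes the request by arm, and no visible visit list provides for it. Nor do the documents show that the capsule-giver's mask is broken, which would require that person to make or learn of such a request. The number of women affected and the size or direction of any reporting bias cannot be worked out.

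The conclusion rests on two assumptions: that treatment location in the masking sentence means allocation, and that no text outside the public file already extends the request to both arms.

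**What to change.** Reword item 6 so that it no longer depends on the arm. For example: every randomised woman of child-bearing potential, in either group, is asked to use hormonal or barrier contraception for 4 months from randomisation. The protocol already takes this approach for omeprazole. Then check that the consent form says the same.

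The cost is one sentence and a consistency check. Visits, sample size and analysis do not change. The small downside is that women on placebo are asked to take a precaution that their own treatment does not call for, which is the price of protecting FMT recipients without disclosing allocation.
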